#### 5.2.8.2.2 AE reporting to the sponsor and timelines

The Investigator must report SAEs, AESIs, and non-serious AEs which are relevant for the reported SAE or AESI, on the BI SAE form via fax immediately (within 24 hours) to the sponsor's unique entry point (country specific contact details will be provided in the ISF). The same timeline applies if follow-up information becomes available. In specific occasions the Investigator could inform the sponsor upfront via telephone. This does not replace the requirement to complete and fax the BI SAE form.

With receipt of any further information to these events, a follow-up SAE form has to be provided. For follow-up information, the same rules and timeline apply as for initial information.

#### 5.2.8.2.3 Information required

All (S)AEs, including those persisting after the individual subject's end of trial, must be followed up until they have resolved, have been sufficiently assessed as 'chronic' or 'stable', or no further information can be obtained.

Proprietary confidential information © 2019 Boehringer Ingelheim International GmbH or one or more of its affiliated companies

#### 5.2.8.2.4 Pregnancy

In rare cases, pregnancy might occur in a clinical trial. Once a subject has been enrolled in the clinical trial and has taken trial medication, the investigator must report any drug exposure during pregnancy in a trial participant immediately (within 24 hours) by means of Part A of the Pregnancy Monitoring Form to the sponsor's unique entry point.

The outcome of the pregnancy associated with the drug exposure during pregnancy must be followed up and reported to the sponsor's unique entry point on the Pregnancy Monitoring Form for Clinical Trials (Part B).

The ISF will contain the Pregnancy Monitoring Form for Clinical Trials (Part A and Part B) as well as non-trial specific information.

As pregnancy itself is not to be reported as an AE, in the absence of an accompanying SAE and/or AESI, only the Pregnancy Monitoring Form for Clinical Trials and not the SAE form is to be completed. If there is an SAE and/or AESI associated with the pregnancy, an SAE form must be completed in addition.

### **5.3 DRUG CONCENTRATION MEASUREMENTS AND PHARMACOKINETICS**

#### **5.3.1 Assessment of pharmacokinetics**

For the assessment of pharmacokinetics, blood and urine samples will be collected at the time points / time intervals indicated in the [Flow Chart](#). The actual sampling times will be recorded and used for determination of pharmacokinetic parameters.

#### **5.3.2 Methods of sample collection**

At a minimum, the sample tube labels should list BI trial number, subject number, visit, and planned sampling time.

After completion of the trial, the plasma samples may be used for further methodological investigations e.g. for stability testing or assessment of metabolites. However, only data related to the analyte and/or its metabolite(s) including anti-drug antibodies (if applicable) will be generated by these additional investigations. The study samples will be discarded after completion of the additional investigations but not later than 5 years after the CTR is archived.

##### **5.3.2.1 Blood sampling for pharmacokinetic analysis of BI 425809**

For quantification of BI 425809 concentrations in plasma, 2.7 mL of blood will be drawn from an antecubital or forearm vein into a K2-EDTA (dipotassium ethylenediaminetetraacetic acid)-anticoagulant blood drawing tube at the times indicated in the [Flow Chart](#). Blood will be withdrawn by means of either an indwelling venous catheter or by venepuncture with a metal needle.

The EDTA-anticoagulated blood samples will be centrifuged for approximately 10 min at approximately 2000 g to 4000 g and at 4 to 8 °C. Two plasma aliquots will be obtained and

Proprietary confidential information © 2019 Boehringer Ingelheim International GmbH or one or more of its affiliated companies

stored in polypropylene tubes. The first aliquot should contain at least 0.5 mL of plasma. The process from blood collection until transfer of plasma aliquots into the freezer should be completed in less than 60 min, with interim storage of blood samples and aliquots on ice. The time each aliquot was placed in the freezer will be documented. Until transfer on dry ice to the analytical laboratory, the aliquots will be stored upright at approximately -20°C or below at the trial site. The second aliquot will be transferred to the analytical laboratory after the bioanalyst has acknowledged safe arrival of the first aliquot. At the analytical laboratory, the plasma samples will be stored at approximately -20°C or below until analysis.

#### 5.3.2.2 Blood sampling for pharmacokinetic analysis of memantine

For quantification of memantine plasma concentrations, 2.7 mL of blood will be taken from an antecubital or forearm vein into a Li-Hep (Lithium-Heparin)-anticoagulant blood drawing tube at the times indicated in the [Flow Chart](#). Blood will be withdrawn by means of either an indwelling venous catheter or by venipuncture with a metal needle. The Li-Hep-anticoagulated blood samples will be centrifuged for about 10 min at about 2000 g to 4000 g and 4 to 8 °C. Two plasma aliquots containing at least 0.5 mL will be obtained and stored in polypropylene tubes. Within a maximum time of 2 hours after sampling at room temperature, the samples should be stored in a freezer. Plasma samples will be stored frozen in an upright position at about -20°C or below until shipment on dry ice to the analytical laboratory. At the analytical laboratory, the plasma samples will be stored at about -20°C or below until analysis.

#### 5.3.2.3 Urine sampling for pharmacokinetic analysis of memantine

A blank urine sample will be collected before administration of trial medication (within 2 h before drug dosing) and two 0.5 mL aliquots will be retained to check for analytical interference by concomitant or rescue medication.

All urine voided during the sampling intervals indicated in the [Flow Chart](#) will be collected in 2 L polyethylene (PE) containers and stored at room temperature. Subjects are told to empty their bladders at the end of each sampling interval. In order to facilitate urine sampling, subjects will be advised to drink at least 100 mL water before the end of each urine sampling interval.

Due to the known adsorption of the drug (its metabolites) to the container wall, 10 mL of 10% Tween 20 solution will be added to each 2 L PE collection container prior to the start of urine sampling. The weight of the empty container will be determined, thereafter 10 mL of 10% Tween 20 will be added, and the weight of the container at the end of each sampling interval will be determined.

The urine weight/volume for each collection interval will be documented (however, no correction for the specific gravity of urine is done, i.e. 1 L is defined to be equal to 1 kg). Two 0.5 mL aliquots will be stored in PP tubes for bioanalytical measurements. If more than one collection container is used in a sampling interval, the contents of all containers have to be mixed before aliquots are prepared. Mixing should be done by transferring the entire content of all collection containers into a single PE/PP or glass container, and stirring the mixed fractions for about 1 min (manually or using a stir bar or other stirring device made of

Proprietary confidential information © 2019 Boehringer Ingelheim International GmbH or one or more of its affiliated companies

PE, PP, Teflon, or glass). Generally, the collection container should be shaken upon addition of every urine fraction to ensure proper distribution of Tween and urine.

At a minimum, the sample tube labels should list BI trial number, subject number, visit, and planned collection time.

Until transfer on dry ice to the analytical laboratory, the urine samples will be stored at approximately -20°C or below at the trial site. The second aliquot will be transferred after the bioanalyst has acknowledged safe arrival of the first aliquot. At the analytical laboratory, the urine samples will be stored at approximately -20°C or below until analysis.

After completion of the trial, the urine samples may be used for further methodological investigations, e.g. for stability testing, assessment of metabolites. However, only data related to the analyte and/or its metabolite(s) will be generated by these additional investigations. The study samples will be discarded after completion of the additional investigations but not later than 5 years after the CTR has been archived.

### **5.3.3 Analytical determinations**

#### **5.3.3.1 Analytical determination of BI 425809 and memantine plasma concentration**

BI 425809 and memantine concentrations in plasma will be determined by a validated LC-MS/MS (liquid chromatography tandem mass spectrometry) assay. All details of the analytical method will be available prior to the start of sample analysis.

#### **5.3.3.2 Analytical determination of memantine urine concentration**

The memantine concentration PK urine study samples will be determined by validated liquid chromatography tandem mass spectrometry assays (LC-MS/MS) at a contracted laboratory with given authorization by BI. All details of the analytical method will be available prior to the start of sample analysis.

### **5.3.4 Pharmacokinetic - pharmacodynamic relationship**

No analysis of the relationship between pharmacokinetic and pharmacodynamic parameters is planned for this trial.

## **5.4 ASSESSMENT OF BIOMARKER**

Not applicable.

## **5.5 BIOBANKING**

Not applicable.

## **5.6 APPROPRIATENESS OF MEASUREMENTS**

All measurements performed during this trial are standard measurements and will be performed in order to monitor subjects' safety and to determine parameters in an appropriate way. The scheduled measurements will allow monitoring of changes in vital signs, standard

Proprietary confidential information © 2019 Boehringer Ingelheim International GmbH or one or more of its affiliated companies

laboratory values, and ECG parameters that might occur because of administration of trial medication. The safety assessments are standard, are accepted for evaluation of safety and tolerability of an orally administered drug, and are widely used in clinical trials. The pharmacokinetic parameters and measurements outlined in [Section 5.3](#) are generally used assessments of drug exposure. The C-SSRS is a validated tool to monitor for suicidality and recommended by the FDA [[R12-4395](#)]. The visual tests (Ishihara plates, Amsler grid test, and visual acuity test) are tests commonly used to assess and monitor the visual sense and have been implemented in previous clinical trials with BI 425809 [[c02820512](#), [c02958024](#)].

## 6. INVESTIGATIONAL PLAN

### 6.1 VISIT SCHEDULE

Exact times of measurements outside the permitted time windows will be documented. The acceptable time windows for screening and the end of trial examination are provided in the [Flow Chart](#).

Study measurements and assessments scheduled to occur ‘before’ trial medication administration, i.e. marked as “pre-dose” (footnote 2 in the [Flow Chart](#)) are to be performed and completed within a 2 h-period prior to the trial drug administration.

The acceptable deviation from the scheduled time for vital signs, C-SSRS, ECG, and laboratory tests will be  $\pm 30$  min.

If scheduled in the [Flow Chart](#) at the same time as a meal, blood sampling, vital signs, visual tests, C-SSRS and 12-lead ECG recordings have to be done first. Furthermore, if several measurements including venepuncture are scheduled for the same time, venepuncture should be the last of the measurements due to its inconvenience to the subject and possible influence on physiological parameters.

For planned blood sampling times and urine collection intervals, refer to the [Flow Chart](#). While these nominal times should be adhered to as closely as possible, the actual sampling times will be recorded and used for the determination of pharmacokinetic parameters.

If a subject misses an appointment, it will be rescheduled if possible. The relevance of measurements outside the permitted time windows will be assessed no later than at the Report Planning Meeting.

### 6.2 DETAILS OF TRIAL PROCEDURES AT SELECTED VISITS

#### 6.2.1 Screening period

After having been informed about the trial, all subjects will provide written informed consent in accordance with GCP and local legislation prior to enrolment in the study.

For information regarding laboratory tests (including drug and virus screening), ECG, vital signs, visual tests, C-SSRS assessment and physical and neurological examination, refer to [Sections 5.2.3 to 5.2.8](#).

#### 6.2.2 Treatment periods

Each subject is expected to participate in 3 treatment periods (Visit 2 - 4).

In the evening of Day -1, and Day 9, Visit 2 study participants will be admitted to the trial site and kept under close medical surveillance until at least 24 h after drug administration on Day 1 and Day 10, respectively.

During Visit 3, subjects will be admitted to the trial site on Day 1 in the morning and remain in-house up to 25 h after the first memantine administration on Day 1, Visit 3. In the evening of Day 34, Visit 3, subjects will again be admitted and stay under close medical surveillance until at least 49 h after the first combined administration of BI 425809 and memantine on

Proprietary confidential information © 2019 Boehringer Ingelheim International GmbH or one or more of its affiliated companies

Day 1, Visit 4. They will be readmitted to the trial site in the evening of Day 9, Visit 4 and discharged not earlier than 24 h after the last drug administration of this trial.

At each discharge subjects will be allowed to leave the trial site after formal assessment and confirmation of their fitness. On all other study days, subjects will be treated in an ambulatory fashion.

The in-house surveillance period can be extended anytime if deemed necessary based on the medical judgement of the investigator.

For details on time points and procedures for collection of plasma and urine samples for PK analysis, refer to [Flow Chart](#) and [Section 5.3.2](#).

The safety measurements performed during the treatment period are specified in [Section 5.3](#) of this protocol and in the [Flow Chart](#). For details on times of all other trial procedures, refer to the [Flow Chart](#). AEs and concomitant therapy will be assessed continuously from screening until the end of trial examination.

On day 18 of Visit 4 (= Period 3) subjects will be contacted by phone and questioned about their well-being.

### 6.2.3 Follow-up period and trial completion

For AE assessment, laboratory tests, recording of ECG and vital signs, and physical examination during the follow-up period, see [Sections 5.2.2](#) to [5.2.8](#).

Subjects who discontinue treatment before the end of the planned treatment period should undergo the EoTrial Visit.

All abnormal values (including laboratory parameters) that are assessed as clinically relevant by the investigator will be monitored using the appropriate tests until a return to a medically acceptable level is achieved. (S)AEs persisting after a subject's EoTrial Visit must be followed until they have resolved, have been sufficiently characterised, or no further information can be obtained.

## 7. STATISTICAL METHODS AND DETERMINATION OF SAMPLE SIZE

### 7.1 STATISTICAL DESIGN – MODEL

The main objectives of this trial are to investigate the relative bioavailability of

- 25 mg of BI 425809 in Steady State when given alone (Reference 1, R1) compared with co-administration of 25 mg of BI 425809 and 20 mg of memantine both in Steady State (Test, T),

and the relative bioavailability of

- 20 mg of memantine in Steady State when given alone (Reference 2, R2) compared with co-administration of 25 mg of BI 425809 and 20 mg of memantine both in Steady State (Test, T),

following oral administration on the basis of the primary pharmacokinetic endpoints, as listed in [Section 2.1.2](#) and [2.1.3](#). The trial is designed to allow intra-subject comparisons and will be evaluated statistically by use of a linear model for logarithmically transformed PK endpoints.

A further objective is to evaluate and compare further pharmacokinetic parameters between the treatments. These pharmacokinetic parameters will be assessed by descriptive statistics.

The assessment of safety and tolerability is a further objective of this trial, and will be evaluated by descriptive statistics for the parameters specified in [Section 2.2.2.2](#).

### 7.2 NULL AND ALTERNATIVE HYPOTHESES

The relative bioavailability of BI 425809 administered alone compared with co-administration with memantine and the relative bioavailability of memantine administered alone compared with co-administration with BI 425809 will be estimated by the ratios of the geometric means (test/reference), and their corresponding 2-sided 90% confidence intervals (CIs) will be provided. This method corresponds to the two one-sided t-test procedure, each at the 5% significance level. Since the main focus is on estimation and not testing, a formal hypothesis test and associated acceptance range is not specified.

### 7.3 PLANNED ANALYSES

#### Analysis sets

Statistical analyses will be based on the following analysis sets:

- Treated set (TS): The treated set includes all subjects who were treated with at least one dose of study drug. The treated set will be used for safety analyses.
- Pharmacokinetic parameter analysis set (PKS): This set includes all subjects in the treated set (TS) who provide at least one PK endpoint that was defined as primary and was not excluded due to a protocol deviations relevant to the evaluation of PK or due

Proprietary confidential information © 2019 Boehringer Ingelheim International GmbH or one or more of its affiliated companies

to PK non-evaluability (as specified in the following subsection ‘Pharmacokinetics’). Thus, a subject will be included in the PKS, even if he/she contributes only one PK parameter value for one period to the statistical assessment. Descriptive and model based analyses of PK parameters will be based on the PKS.

Adherence to the protocol will be assessed by the trial team. Important protocol deviations (IPD) categories will be suggested in the IQRM plan. IPDs will be identified no later than in the Report Planning Meeting, and the IPD categories will be updated as needed.

### Pharmacokinetics

The pharmacokinetic parameters listed in [Section 2.1](#) for drug BI 425809 will be calculated according to the relevant SOP of the Sponsor ([001-MCS-36-472](#)).

Plasma concentration data and parameters of a subject will be included in the statistical pharmacokinetic (PK) analyses if they are not flagged for exclusion due to a protocol deviation relevant to the evaluation of PK (to be decided no later than in the Report Planning Meeting) or due to PK non-evaluability (as revealed during data analysis, based on the criteria specified below). Exclusion of a subject’s data will be documented in the CTR.

Relevant protocol violations may be

- Incorrect trial medication taken, i.e. the subject received at least one dose of trial medication the subject was not assigned to
- Incorrect dose of trial medication taken
- Use of restricted medications

Plasma concentrations and/or parameters of a subject will be considered as non-evaluable, if for example

- The subject experienced emesis that occurred at or before two times median  $t_{max}$  of the respective treatment (Median  $t_{max}$  is to be determined excluding the subjects experiencing emesis),
- The subject experiences emesis at any time during the labelled dosing interval
- A predose concentration is  $>5\% C_{max}$  value of that subject
- Missing samples/concentration data at important phases of PK disposition curve

Plasma concentration data and parameters of a subject which is flagged for exclusion will be reported with its individual values but will not be included in the statistical analyses. Descriptive and inferential statistics of PK parameters will be based on the PKS.

Only concentration values within the validated concentration range and actual sampling times will be used for the calculation of pharmacokinetic parameters. Concentrations used in the pharmacokinetic calculations will be in the same format provided in the bioanalytical report, (that is, to the same number of decimal places provided in the bioanalytical report).

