#### 1.2.1.4 Clinical pharmacokinetics

After administration of BI 425809 tablets, maximum plasma concentrations of BI 425809 occurred around 3 to 5 h after dosing. The terminal half-life was independent of the administered dose and ranged from 37 to 59h. Exposure increased in the tested dose range of 5 to 75 mg but with a trend to a less than dose proportional behaviour for doses of 50 mg and above. Food increased drug exposure (fed/fast ratio for  $C_{max}$ : 142%, for  $AUC_{0-tz}$ : 126%).

Steady state was reached after 6 days of BI 425809 dosing with accumulation ratios for  $C_{max}$  ranging from 1.96 to 2.63 and for AUC from 2.31 to 3.21. No exposure difference between

Proprietary confidential information © 2019 Boehringer Ingelheim International GmbH or one or more of its affiliated companies

young and elderly healthy subjects was observed. Furthermore, pharmacokinetics in Japanese and Chinese subjects were comparable with Caucasians.

As BI 425809 is a substrate of CYP3A4, co-administration of weak, moderate and strong CYP3A4 inhibitors and inducers is not permitted.

Due to a mild induction potential for CYP3A4 [[c08949593](#)], BI 425809 should be administered with caution in presence of sensitive substrates of these enzymes, and sensitive CYP3A4 substrates with a narrow therapeutic index are not permitted. BI 425809 had no relevant effect on CYP2C9, CYP2C19, and P-gp substrates.

In plasma from young and elderly healthy volunteers administered single or multiple oral doses of BI 425809 (10, 25 and 50 mg) (trials 1346.1 and 1346.2), four oxidative metabolites, M526, M528, BI 758790, and M544 and two metabolites resulting from hydrolysis of the amide bond, BI 761036 and M312 (IN00079211), were identified. BI 761036 was with 54% the main contributor to plasma drug-related exposure, BI 758790 occurs at plasma exposures similar to parent, each made up around 20% of total drug-related exposure.

For a more detailed description of the BI 425809 profile please refer to the current Investigator's Brochure [[c02155957](#)].

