#### 1.2.2.3 Clinical pharmacokinetics

After oral administration in humans, memantine is completely absorbed with an absolute bioavailability of approximately 100%. There is no indication that food influences the absorption of memantine.  $T_{max}$  is between 3 and 8 hours and memantine has demonstrated linear pharmacokinetics in the dose range of 10 to 40 mg in healthy volunteers [[R18-3740](#), [R18-3739](#)].

Daily doses of 20 mg lead to steady-state plasma concentrations of memantine ranging from 70 to 150 ng/ml (0.5 - 1  $\mu$ mol/L) with large interindividual variations. When daily doses of 5 to 30 mg were administered, a mean cerebrospinal fluid (CSF)/serum ratio of 0.52 was calculated. The volume of distribution is around 10 l/kg. About 45% of memantine is bound to plasma-proteins.

In humans, about 80% of the circulating memantine-related material is present as the parent compound. Main human metabolites are N-3,5-dimethyl-gludantan, the isomeric mixture of 4- and 6-hydroxy-memantine, and 1-nitroso-3,5-dimethyl-adamantane. None of these metabolites exhibit NMDA-antagonistic activity. No cytochrome P450-catalysed metabolism has been detected *in vitro* and memantine did not inhibit CYP1A2, 2A6, 2C9, 2D6, 2E1, 3A, Flavin-containing monooxygenase, epoxide hydrolase or sulphation *in vitro*. [[R18-3740](#), [R18-3739](#)]

Unchanged memantine is mainly excreted renally with a terminal  $t_{1/2}$  of 60 to 100 hours. Tubular secretion as well as tubular reabsorption are involved in its renal elimination. In vitro data suggest a potential role of MATE1 and OCT2 for renal secretion of memantine [[R17-3276](#), [R15-0935](#)] and also indicate that both, MATE1 and to an even higher extent OCT2, are inhibited by memantine, albeit with reported IC50 values that exceed unbound plasma concentrations expected during therapy [[R17-3276](#)]. The renal elimination rate of memantine under alkaline urine conditions may be reduced by a factor of up to 7 to 9. Alkalisation of urine may result from drastic changes in diet, e.g. from a carnivore to a vegetarian diet. Therefore, concomitant use of drugs that have an alkalinizing effect on the urinary pH, e.g. massive ingestion of alkalinising gastric buffers, or that compete at / inhibit the transporters of the renal cation transporter system (OCT2, MATE1) may theoretically lead to

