#### **2.1.2 Primary endpoints**

The following pharmacokinetic parameters will be determined for BI 425809 and for memantine:

- $AUC_{\tau,ss}$  (area under the concentration-time curve of the analyte in plasma at steady state over a uniform dosing interval  $\tau$ )
- $C_{max,ss}$  (maximum measured concentration of the analyte in plasma at steady state over a uniform dosing interval  $\tau$ )

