7.4 PRIMARY ENDPOINTS

7.4.1 Primary analysis of the primary endpoints

Primary analysis of the primary endpoints will be performed as defined in Sections 7.3.1 of the CTP.

The statistical model for the primary analysis defined in the CTP is an analysis of variance (ANOVA) model on the logarithmic scale including "treatment" as fixed effects and "subject" as random effect. Relative bioavailability of the study treatments will be estimated by the ratios of the geometric means of (T/R1) and (T/R2) of the primary endpoints.

Exclusion of PK parameters

The ADS ADPP contains column variables APEXC and APEXCO indicating inclusion/exclusion (APEXC) of a PK parameter and an analysis flag comment (APEXCO). All analyses based on the PKS are based on PK parameter values which are not flagged for exclusion, i.e. with APEXC equal to "Included".

Exclusion of plasma concentrations

The ADS ADPC (PK concentrations per time-point or per time-interval) contains column variables ACEXC or ACEXCO indicating inclusion/exclusion (ACEXC) of a concentration and an analysis flag comment (ACEXCO). Exclusion of a concentration depends on the analysis flag comment ACEXCO. For example, if ACEXCO is set to "ALL CALC", the value will be excluded for all types of analyses based on concentrations. If ACEXCO is set to "DESC STATS" the value will be excluded from descriptive evaluations per planned time

point/time interval. If ACEXCO contains the addition "TIME VIOLATION" or "TIME DEVIATION", the value can be used for further analyses based on actual times. If ACEXCO is set to "HALF LIFE", the value will be excluded from half-life calculation only; the value is included for all other analyses. Excluded concentration itself will be listed in the CTR associated with an appropriate flag.

Further details are given in "Noncompartmental Pharmacokinetic / Pharmacodynamic Analyses of Clinical Studies" (4) and "Description of Analytical Transfer Files and PK/PD Data Files" (5).

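### The rule excluding profiles with a predose level above 5% of Cmax would, as written, remove essentially every steady-state primary profile and empty the PK analysis set

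*Protocol*

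**What the plan says.** Protocol Section 7.3, subsection Pharmacokinetics, introduces its list with "Plasma concentrations and/or parameters of a subject will be considered as non-evaluable, if for example". The third item is "A predose concentration is $>5\% C_{max}$ value of that subject". It names no day, dose or type of profile. Data flagged under this subsection are listed individually but left out of the statistical analyses.

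The list decides who enters the primary analysis. The PKS definition in the same section requires at least one primary PK endpoint that has not been excluded for non-evaluability, and it points to this subsection for the criteria. The bar is otherwise low: "Thus, a subject will be included in the PKS, even if he/she contributes only one PK parameter value for one period".

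The primary endpoints in Protocol Section 2.1.2 are AUCtau,ss and Cmax,ss of both analytes; the latter is the "maximum measured concentration of the analyte in plasma at steady state over a uniform dosing interval". There are no others.

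The SAP states in Section 4 that it follows the protocol's methods, takes over the protocol's subject sets in Section 6.3, and says in Section 7.4.1: "All analyses based on the PKS are based on PK parameter values which are not flagged for exclusion". Neither Section 7.4.1 nor Table 6.2:1 limits the 5% condition.

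**The concern.** A 5% predose limit is a carry-over check. It asks whether drug from an earlier period contaminates a profile that ought to start from zero. The primary profiles in this trial (Visit 2 Day 10, Visit 3 Day 35, Visit 4 Day 10) are meant to start from a high trough, because the design doses both drugs to steady state. A high predose level there shows that dosing worked.

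Taken literally, the criterion would exclude the very profiles the trial was run to obtain. If it is not taken literally, someone has to decide at or after the Report Planning Meeting, with concentrations available in an open-label trial, where a written exclusion rule applies and where it does not.

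**Working it through.** **Inputs (all from the protocol)**
- Dosing interval 24 h for both drugs. The predose sample on the steady-state profile days is taken within 10 min before the next dose (Flow Chart, footnote 8).
- BI 425809 (Section 1.2.1.4): "The terminal half-life was independent of the administered dose and ranged from 37 to 59h"; tmax 3 to 5 h; accumulation ratio 1.96 to 2.63 for Cmax and 2.31 to 3.21 for AUC.
- Memantine (Section 1.2.2.3): "Unchanged memantine is mainly excreted renally with a terminal" half-life of 60 to 100 h; tmax 3 to 8 h. Period 3 follows Period 2 without washout.
- N = 16.

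**1. The plan's own figure.** Table 7.7:1 gives a precision at N = 16 of 1.208 (gCV 24%) and 1.063 (gCV 7.7%). With s = sqrt(ln(1 + gCV²)), the log half-width is

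w = t(0.95, 15) × s × sqrt(2/16) × sqrt(chi²(0.95, 15)/15).

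Then exp(w) = 1.2085 and 1.0634. All 16 rows of the table reproduce. The sample-size calculation is sound, but it presumes evaluable profiles from 16 subjects.

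**2. Predose/Cmax at steady state, bolus limit:** exp(−ln2 × 24 / t½).

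**3. With absorption.** One-compartment oral model, with ka solved so that ln(ka/k)/(ka − k) equals the stated tmax, and doses superposed (10 doses for BI 425809, full steady state for memantine).

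| Analyte | t½ (h) | Bolus limit | Oral model, over the tmax range |
|---|---|---|---|
| BI 425809 | 37 | 0.638 | 0.670–0.696 |
| BI 425809 | 59 | 0.754 | 0.763–0.780 |
| Memantine | 60 | 0.758 | 0.782–0.822 |
| Memantine | 100 | 0.847 | 0.862–0.885 |

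Using the actual memantine titration with the bolus form gives 0.756–0.841 on Visit 3 Day 35 and 0.758–0.846 on Visit 4 Day 10.

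**4. A check that does not use the half-life.** Under superposition, Cmax,ss cannot exceed the first-dose Cmax plus the predose level. Hence predose/Cmax,ss ≥ 1 − 1/Rac. With the Cmax ratios for BI 425809: 1 − 1/1.96 = 0.49 and 1 − 1/2.63 = 0.62.

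**5. Distance from the limit.** 0.49/0.05 = 9.8 and 0.885/0.05 = 17.7, so about 10 to 18 times.

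**6. What would pass.** The bolus form requires t½ ≤ 24 × ln2 / ln20 = 5.55 h. Counting decline only from a tmax of 3 h or 8 h gives 21 × ln2 / ln20 = 4.86 h or 16 × ln2 / ln20 = 3.70 h.

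**7. Between-subject spread.** The documents give no CV for half-life, so this step is an assumption: lognormal, with the median at the value shown. The third and fourth rows use 29.3 h, the effective half-life implied by the lowest AUC accumulation ratio: 24 × ln2 / −ln(1 − 1/2.31).

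| Median t½ | CV | P(t½ ≤ 5.55 h), one subject |
|---|---|---|
| 37 h (BI 425809) | 30% | 5 × 10⁻¹¹ |
| 37 h (BI 425809) | 50% | 3 × 10⁻⁵ |
| 29.3 h (BI 425809) | 50% | 2 × 10⁻⁴ |
| 29.3 h (BI 425809) | 100% | 0.023 |
| 60 h (memantine) | 50% | 2 × 10⁻⁷ |

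Even the extreme fourth row leaves an expected 16 × 0.023 ≈ 0.4 subjects with an evaluable BI 425809 profile.

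**The case against.** The best counter-argument is that the list only gives examples and mixes types of profile. It holds two emesis criteria, one tied to twice median tmax and one to the whole dosing interval. Twice the stated tmax is at most 16 h, inside the 24 h interval, so the first would be redundant if both applied everywhere. Each example may therefore be meant for the profile it suits, and the trial does have first-dose profiles (Visit 2 Day 1, Visit 3 Day 1). Flagging details are also left to sponsor standards that are not part of these documents. Finally, if every profile of every treatment breaches the limit, waiving the rule uniformly selects no subject and favours no treatment.

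Some of this stands. The mixed-list reading is a plausible account of the intent, and an empty PKS is what the text prescribes rather than a forecast of what the team would do. The uniform-waiver point also stands: no route to a biased ratio is shown, so the worry about a data-aware choice is minor.

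The rest does not rescue the text. Giving examples leaves the list open to further reasons; it does not switch off those listed. Nothing assigns the 5% condition to first-dose profiles, and unseen standards cannot be credited with doing so. Reading it as the first dose of each period still fails for memantine, which enters Period 3 at steady state. First-dose profiles yield no primary endpoint, so they cannot keep a subject in the PKS.

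**Conclusion.** The concern holds. The criterion is wrong as written for this design, and it governs the primary analysis: an expected 0 of 16 subjects would keep a primary endpoint for either analyte, so the primary objective could not be met under the plan's own rule. This rests on the protocol's half-lives, tmax ranges and accumulation ratios, on linear superposition, and on reading the listed conditions as triggers. The margin is wide enough that the choice of PK model does not matter, and only an extreme assumed spread of half-lives would let an occasional subject through.

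The realistic cost is less dramatic but still needs removing. The team would have to set aside a stated exclusion criterion that essentially every profile meets, without having declared it, and explain that in the trial report. It must be fixed before the analysis, because the exclusion rule and the primary endpoints cannot both stand.

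**What to change.** In Protocol Section 7.3 (Pharmacokinetics), or as a declared change in SAP Section 4, restrict the 5% predose condition to the first-dose profiles: Visit 2 Day 1 for BI 425809 and Visit 3 Day 1 for memantine. State that it does not apply to AUCtau,ss or Cmax,ss on Visit 2 Day 10, Visit 3 Day 35 or Visit 4 Day 10. Repeat the exemption in SAP Section 7.4.1 under the exclusion of PK parameters.

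If an evaluability check is wanted on the steady-state days, name one that fits, such as documented complete dosing over the preceding days or a trough-attainment check. The former overlaps with supervised dosing and the existing protocol-deviation categories, so a cross-reference may be enough. The BI 425809 predose sample on Visit 4 Day 1 could be reviewed separately for carry-over. Little is expected: at least 7 + 35 = 42 days after the last Period 1 dose, the residue at a 59 h half-life is 2^(−1008/59) ≈ 7 × 10⁻⁶ of the earlier level.

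The cost is one sentence in each place. Sampling, data and procedures are unchanged, all 16 subjects remain eligible for the PKS, and the precision in Table 7.7:1 is unaffected.
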